5.3 Major Events

Major events are non-treatment-related grade 3 or 4 hematologic and non-hematologic adverse events. Treatment should be delayed for major events if pamiparib (BGB-290) may further complicate the non-treatment-related event. If a major event requires a delay of treatment, treatment must be delayed until the event is resolved (\leq grade 1 or \leq baseline). If the event is not resolved in \leq 28 days, the patient will be removed from treatment. The ABTC Central Office should be consulted if you are not clear on whether to continue or delay treatment.

5.4 Use of Hematologic Growth Factors

No growth factors (G-CSF or GM-CSF) are to be used prophylactically in this protocol. Clinicians caring for patients on this protocol are permitted to use these growth factors to provide optimal care for patients with severe neutropenia in accordance with the ASCO guidelines, (JCO, 12, 1994: pp2471-2508). If these growth factors are used in the acute setting of neutropenia and infection (documented or suspected), they will not be utilized prophylactically in subsequent cycles and they will not subsequently be used *in lieu* of dose reduction of pamiparib (BGB-290) or TMZ.

5.5 Toxicity Criteria

All toxicities will be described and graded according to the NCI Common Terminology Criteria for Adverse Events (CTCAE) version 5.0. All appropriate treatment areas should have access to a copy of the CTCAE version 5.0. A copy of the CTCAE version 5.0 can be downloaded from the CTEP web site

(http://ctep.cancer.gov/protocolDevelopment/electronic_applications/ctc.htm). See also Section 9.2.1, Recording of Adverse Events.

6.0 PHARMACEUTICAL INFORMATION

6.1 Pamiparib (BGB-290) (NSC# 803412)

Chemical Name: (R)-2-fluoro-10a-methyl-5,8,9,10,10a,11-hexahydro-5,6,7a,11-tetraazyacyclohepta[def]cyclopenta[a]fluoren-4(7H)-one

Molecular Formula: C₁₆H₁₅FN₄O

Molecular Mass: 298

Mode of Action: highly potent and selective PARP inhibitor, binds to PARP enzyme and prevents PARP-mediated repair of single-stranded DNA breaks via base-excision repair, thus enhancing the accumulation of DNA double strand breaks.

NCI # ABTC-1801

PI: [name]

How Supplied: supplied by BeiGene Ltd. pamiparib (BGB-290) pellet-in-capsules are provided in a container with a child-resistant closure. Each container is labeled with space to enter the subject's ID, treatment and period number. The label is pre-printed and includes content and quantity of pamiparib (BGB-290), protocol number, batch number, administration instructions, storage instructions and expiry date. Subjects will receive pamiparib (BGB-290) as 10 mg, 20 mg or 40 mg capsules, depending on dose level and availability.

Storage: Pamiparib (BGB-290) must be kept at 15°C to 30°C. An accurate study drug accountability log must be maintained and kept up to date at all times.

Stability: Pamiparib (BGB-290) is an oral formulation. The drug should be stable at minimum until the expiration date on the bottle.

Route of Administration: Pamiparib (BGB-290) is taken by mouth with 8 ounces of water while fasting.

Known Potential Drug Interactions: Strong and moderate CYP3A inhibitors and strong CYP3A inducers are prohibited due to potential for drug interactions. Strong CYP2C8 inhibitors and sensitive CYP2C9 substrates or CYP2C9 substrates with narrow therapeutic index should be used with caution.

Contraindications: Pamiparib (BGB-290) should not be used in patients who are pregnant.

6.1.1 Agent Ordering

Pamiparib (BGB-290) may be requested by eligible participating Investigators (or their authorized designee) at each participating institution. The eligible participating investigators at each participating institution must be registered with CTEP, DCTD through an annual submission of FDA Form 1572 (Statement of Investigator), NCI Biosketch, Agent Shipment Form, and Financial Disclosure Form (FDF).

Once a site has submitted all required regulatory documents to ABTC and BeiGene (Form 1572, curriculum vitae, licenses, IRB approval of protocol and consent), an initial supply of drug can be ordered. An ABTC drug order form, which can be found on the ABTC website (ABTConsortium.org), should be emailed to the ABTC Central Office to initiate sending of the drug. The ABTC Central Office will forward the drug order form to BeiGene. Please allow 7 days from the receipt of the drug order form at BeiGene for drug shipment.

6.1.2 Agent Accountability

Each institutional Investigator, or a responsible party designated by the Investigator, agrees to supply drugs only to those subjects enrolled in the study and must maintain a careful record of the inventory and disposition of all drugs received from BeiGene, using the NCI Investigational Drug Accountability Record Form. Upon termination of the study, the

ABTC # 1801	NCI # ABTC-1801	PI: [name]

Investigator or designee must complete a final inventory of supplies.

6.2	Temozolomide	
	Generic name:	Temozolomide
	Commercial name:	Temodar®
	Chemical name:	3,4-dihydro-3-methyl-4-oxoimidazo[5,1-d]- as -tetrazine-8 carboxamide
	Classification	Antineoplastic agent, alkylating
	Molecular Formula:	C6H6N6O2
	Molecular Weight:	194.15
	Mechanism of Action:	Temozolomide is not directly active but undergoes rapid nonenzymatic conversion at physiologic pH to the reactive compound 5-(3-methyltriazen-1-yl)- imidazole-4-carboxamide (MTIC). The cytotoxicity of MTIC is thought to be primarily due to alkylation of DNA. Alkylation (methylation) occurs mainly at the O^6 and N^7 positions of guanine.
	Appearance:	White to light tan/light pink powder
	Melting point:	Decomposes at 206°C
	How Supplied:	Commercially available
	Stability:	The molecule is stable at acidic pH (<5), and labile at pH >7, hence TEMODAR can be administered orally. The prodrug, temozolomide, is rapidly hydrolyzed to the active 5-(3-methyltriazen-1- yl)imidazole-4-carboxamide (MTIC) at neutral and alkaline pH values, with hydrolysis taking place even faster at alkaline pH. The product label recommends Storage at 25°C (77°F); excursions permitted to 15°-30°C (59°-86°F).
	Half life:	Temozolomide is rapidly eliminated with a mean elimination half-life of 1.8 hours

NCI # ABTC-1801

PI: [name]

Packaging, Dispensing and Storage

Temozolomide capsules are available in 5-mg, 20-mg, and 100-mg, strengths. The capsules contain a white capsule body with a color cap and the colors vary based on the dosage strength. The 5-mg, 20-mg, 100-mg capsule strengths are available in 5-count and 14-count packages. The product label recommends Storage at 25°C (77°F); excursions permitted to 15°-30°C (59°-86°F). Labeling of the packages containing the capsules will be done in accordance with the local procedures (as required by law). According to the dosing the hospital pharmacist delivers the temozolomide dosage for a complete cycle to the subject.

7.0 PROCEDURES FOR PATIENT ENTRY ON STUDY

This study is supported by the NCI Cancer Trials Support Unit (CTSU) Regulatory Office and uses the Oncology Patient Enrollment Network (OPEN).

7.1 CTEP Registration Procedures

Investigator and Research Associate Registration with CTEP

Food and Drug Administration (FDA) regulations require IND sponsors to select qualified investigators. NCI policy requires all persons participating in any NCIsponsored clinical trial to register and renew their registration annually. To register, all individuals must obtain a CTEP Identity and Access Management (IAM) account (https://ctepcore.nci.nih.gov/iam). In addition, persons with a registration type of Investigator (IVR), Non-Physician Investigator (NPIVR), or Associate Plus (AP) (*i.e.*, clinical site staff requiring write access to Oncology Patient Enrollment Network (OPEN) or Rave or acting as a primary site contact) must complete their annual registration using CTEP's web-based Registration and Credential Repository (RCR) (https://ctepcore.nci.nih.gov/rcr). Documentation requirements per registration type are outlined in the table below.

ABTC #	1801
--------	------

NCI # ABTC-1801

PI: [name]

Documentation Required	IVR	NPIVR	AP	А
FDA Form 1572	~	~		
Financial Disclosure Form	~	~	~	
NCI Biosketch (education, training, employment, license, and certification)	*	~	*	
HSP/GCP training	~	~	~	
Agent Shipment Form (if applicable)	~			
CV (optional)	~	~	~	

Additional information can be found on the CTEP website at <

https://ctep.cancer.gov/investigatorResources/default.htm >. For questions, please contact the RCR *Help Desk* by email at < [contact] >.

An active CTEP-IAM user account and appropriate RCR registration is required to access all CTEP and Cancer Trials Support Unit (CTSU) websites and applications. In addition, IVRs and NPIVRs must list all clinical practice sites and IRBs covering their practice sites on the FDA Form 1572 in RCR to allow the following:

- Added to a site roster
- Assigned the treating, credit, consenting, or drug shipment (IVR only) tasks in OPEN
- Act as the site-protocol PI on the IRB approval
- Assigned the Clinical Investigator (CI) role on the Delegation of Tasks Log (DTL).

7.2 Site Registration Requirements – Institutional Review Board Approval

Each investigator or group of investigators at a clinical site must obtain IRB approval for this protocol and submit IRB approval and supporting documentation to the CTSU Regulatory Office before they can be approved to enroll patients. Assignment of site registration status in the CTSU Regulatory Support System (RSS) uses extensive data to make a determination of whether a site has fulfilled all regulatory criteria including but not limited to the following:

ABTC # 1801

PI: [name]

- An active Federal Wide Assurance (FWA) number
- An active roster affiliation with the Lead Network or a participating organization
- A valid IRB approval
- Compliance with all protocol specific requirements.

In addition, the site-protocol Principal Investigator (PI) must meet the following criteria:

- Active registration status
- The IRB number of the site IRB of record listed on their Form FDA 1572
- An active status on a participating roster at the registering site.

Sites participating on the NCI CIRB initiative that are approved by the CIRB for this study are not required to submit IRB approval documentation to the CTSU Regulatory Office. For sites using the CIRB, IRB approval information is received from the CIRB and applied to the RSS in an automated process. Signatory Institutions must submit a Study Specific Worksheet for Local Context (SSW) to the CIRB via IRB Manager to indicate their intent to open the study locally. The CIRB's approval of the SSW is then communicated to the CTSU Regulatory Office. In order for the SSW approval to be processed, the Signatory Institution must inform the CTSU which CIRB-approved institutions aligned with the Signatory Institution are participating in the study.

Requirements For ABTC-1801 Site Registration:

• IRB approval (For sites not participating via the NCI CIRB; local IRB documentation, an IRB-signed CTSU IRB Certification Form, Protocol of Human Subjects Assurance Identification/IRB Certification/Declaration of Exemption Form, or combination is accepted)

Submitting Regulatory Documents:

Submit required forms and documents to the CTSU Regulatory Office, where they will be entered and tracked in the CTSU RSS.

Regulatory Submission Portal: www.ctsu.org (members' area) \rightarrow Regulatory Tab \rightarrow Regulatory Submission

When applicable, original documents should be mailed to:

CTSU Regulatory Office [name]

Institutions with patients waiting that are unable to use the Portal should alert the CTSU Regulatory Office immediately at [name] in order to receive further instruction and support.

ABTC # 1801

NCI # ABTC-1801

PI: [name]

Checking Your Site's Registration Status:

You can verify your site registration status on the members' section of the CTSU website.

- Go to https://www.ctsu.org and log in to the members' area using your CTEP-IAM username and password
- Click on the Regulatory tab
- Click on the Site Registration tab
- Enter your 5-character CTEP Institution Code and click on Go

Note: The status given only reflects compliance with IRB documentation and institutional compliance with protocol-specific requirements as outlined by the Lead Network. It does not reflect compliance with protocol requirements for individuals participating on the protocol or the enrolling investigator's status with the NCI or their affiliated networks.

7.3 Patient Registration

Patient enrollment will be facilitated using OPEN. All site staff will use OPEN. OPEN is a web-based registration system available for ABTC studies from 9 a.m. to 4:30 p.m. Eastern Time. To access OPEN, the site user must have an active CTEP-IAM account (check at < https://ctepcore.nci.nih.gov/iam >) and a 'Registrar' role on either the LPO or participating organization roster. Registrars must hold a minimum of an AP registration type.

All site staff will use OPEN to enroll patients to this study. It is integrated with the CTSU Enterprise System for regulatory and roster data and, upon enrollment, initializes the patient in the Rave database. OPEN can be accessed at https://open.ctsu.org or from the OPEN tab on the CTSU members' side of the website at https://www.ctsu.org. To assign an IVR or NPIVR as the treating, crediting, consenting, drug shipment (IVR only), or investigator receiving a transfer in OPEN, the IVR or NPIVR must list on their Form FDA 1572 in RCR the IRB number used on the site's IRB approval.

Since this study includes a Phase I component, patient enrollment for this study will be facilitated using the Slot-Reservation System in conjunction with the registration system on OPEN. Prior to discussing protocol entry with the patient, all site staff must use the CTSU OPEN Slot Reservation System to ensure that a slot on the protocol is available to the patient. Once a slot- reservation confirmation is obtained, site staff may then proceed to enroll patients to this study.

Prior to accessing OPEN, site staff should verify the following:

- All eligibility criteria have been met within the protocol stated timeframes. Site staff should use the registration forms provided on the group web site as a tool to verify eligibility.
- All patients have signed an appropriate consent form and HIPAA authorization form (if applicable).

ABTC # 1801

PI: [name]

Access requirements for OPEN:

- Site staff will need to be registered with CTEP and have a valid and active CTEP-IAM account. This is the same account (user id and password) used for credentialing in the CTSU members' web site.
- To perform registrations, the site user must have been assigned the 'Registrar' role (or equivalent) on the relevant Group or CTSU roster.

The OPEN system will provide the site with a printable confirmation of registration and treatment information. Upon completion of the registration process in OPEN, sites must contact the ABTC Central Office to obtain confirmation of the patient's registration and dose assignment. The local investigational pharmacy should call the ABTC Central Office to confirm the actual dose prior to dispensing the first dose of the first cycle. No patient may begin treatment until registration AND dose have been confirmed by the ABTC Central Office.

Further instructional information is provided on the CTSU members' web site OPEN tab or within the OPEN URL (https://open.ctsu.org). For any additional questions contact the CTSU Help Desk at [name] or [contact].

8.0 Response Assessment / Safety and Quality Assurance

8.1 Criteria for Response Assessment

Patients with measurable enhancing disease will be assessed by the high grade glioma (HGG) RANO (radiographic assessment in neuro-oncology) criteria⁶⁴, while patients with only T2/FLAIR abnormalities will be assessed by the low grade glioma (LGG) RANO criteria^{63.} For the purposes of this study, subjects should be re-evaluated at the end of every 2 cycles (approximately every 8 weeks) with a contrast-enhanced cranial MRI scan. The response will be determined as outlined in the RANO criteria below. As a reminder, all assessments should be in compliance with the Imaging Core Manual.

Measurable disease. Bi-dimensionally, contrast-enhancing, measurable lesions with clearly defined margins by MRI scan, with a minimal size of 1 cm x 1 cm, and visible on 2 axial slices which are at least 5 mm apart with 0 mm skip. Measurement of tumor around a cyst or surgical cavity, if necessary, requires a minimum thickness of 3 mm. If there are >2 lesions (multifocal) at baseline, the investigator must choose the largest two to be followed before a participant is entered on study. The remaining lesions will be considered non-measureable for the purpose of objective response determination. Unless progression is observed, objective response can only be determined when all measurable and non-measurable lesions are assessed.

ABTC # 1801

NCI # ABTC-1801

PI: [name]

8.1.1 HGG RANO

Complete Response – CR (requires *all* of the following):

a) Complete disappearance of all enhancing measurable and non-measurable disease sustained for at least 4 weeks. In the absence of a confirming scan 4 weeks later, this scan will be considered only stable disease.

b) No new lesions.

c) All measurable and non-measurable lesions must be assessed using the same techniques as baseline.

- d) Subjects must be off corticosteroids (or on physiologic replacement doses only).
- e) Stable or improved non-enhancing (T2/FLAIR) lesions.
- f) Stable or improved clinically.

Note: Subjects with non-measurable disease cannot have a complete response. The best response possible is stable disease.

Partial Response – PR (requires *all* of the following):

a) Greater than or equal to 50% decrease compared to baseline in the sum of products of perpendicular diameters of all measurable enhancing lesions sustained for at least 4 weeks. In the absence of a confirming scan 4 weeks later, this scan will be considered only stable disease.

- b) No progression of non-measurable disease.
- c) No new lesions.

d) All measurable and non-measurable lesions must be assessed using the same techniques as baseline.

e) The corticosteroid dose at the time of the scan evaluation should be no greater than the dose at time of baseline scan.

f) Stable or improved non-enhancing (T2/FLAIR) lesions on same or lower dose of corticosteroids compared to baseline scan.

g) Stable or improved clinically.

Note: Subjects with non-measurable disease cannot have a partial response. The best response possible is stable disease.

Stable Disease – SD (requires *all* of the following):

a) Does not qualify for CR, PR, or progressive disease (PD).

b) The designation of stable disease requires a minimum of 4-week duration.

c) All measurable and non-measurable sites must be assessed using the same techniques as baseline.

d) Stable non-enhancing (T2/FLAIR) lesions on same or lower dose of corticosteroids compared to baseline scan. In the event that the corticosteroid dose was increased for new symptoms and signs without confirmation of disease progression on neuroimaging, and subsequent follow-up imaging shows that this increase in

NCI # ABTC-1801

PI: [name]

corticosteroids was required because of disease progression, the last scan considered to show stable disease will be the scan obtained when the corticosteroid dose was equivalent to the baseline dose.

e) Stable clinically.

Progressive Disease – PD (defined by *any* of the following):

a) $\geq 25\%$ increase in sum of the products of perpendicular diameters of enhancing lesions compared to the smallest tumor measurement obtained either at baseline (if no decrease) or best response, on stable or increasing doses of corticosteroids.*

b) Significant increase in T2/FLAIR non-enhancing lesion on stable or increasing doses of corticosteroids compared to baseline scan or best response following initiation of therapy,* not due to co-morbid events (radiation therapy, demyelination, ischemic injury, infection, seizures, postoperative changes, or other treatment effects).

c) Any new lesion.

d) Clear clinical deterioration not attributable to other causes apart from the tumor (e.g., seizures, medication adverse effects, complications of therapy, cerebrovascular events, infection, etc.) or changes in corticosteroid dose. The definition of clinical deterioration is left to the discretion of the treating physician, but it is recommended that a decrease in 20% of KPS or from any baseline to 50% or less be considered, unless attributable to comorbid events.

- e) Failure to return for evaluation due to death or deteriorating condition.
- f) Clear progression of non-measurable disease.

* Stable doses of corticosteroids include patients not on corticosteroids.

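### The HGG RANO notes under CR and PR omit the word *only*, so as written they bar patients with measurable enhancing disease plus extra or small lesions from counting as responders

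*Combined protocol and SAP*

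**What the plan says.** The two notes, both in Section 8.1.1 (HGG RANO):

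- Under CR: "Note: Subjects with non-measurable disease cannot have a complete response. The best response possible is stable disease".
- Under PR: "Note: Subjects with non-measurable disease cannot have a partial response. The best response possible is stable disease".

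The criteria to which the notes are attached:

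- CR (a): "Complete disappearance of all enhancing measurable and non-measurable disease sustained for at least 4 weeks".
- PR (b): "No progression of non-measurable disease".
- CR (c) and PR (d) require non-measurable as well as measurable lesions to be re-assessed with the baseline technique.

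Section 8.1 decides which lesions are non-measurable:

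- A measurable lesion must be contrast-enhancing, "with a minimal size of 1 cm x 1 cm, and visible on 2 axial slices".
- Where there are many lesions: "If there are >2 lesions (multifocal) at baseline, the investigator must choose the largest two to be followed before a participant is entered on study". What becomes of the others is stated next: "The remaining lesions will be considered non-measureable for the purpose of objective response determination".
- On patients who have both kinds of lesion, the section says: "Unless progression is observed, objective response can only be determined when all measurable and non-measurable lesions are assessed".

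Section 8.1 sends patients with measurable enhancing disease to HGG RANO and those with only T2/FLAIR abnormality to LGG RANO. Section 8.1.2 (LGG RANO) has no such note. Section 11 makes CR+PR the primary endpoint of Arms A and B and takes its definition from Section 8.

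**The concern.** The listed criteria tell the reader what non-measurable disease must do for a response to be declared: disappear for CR, not progress for PR. The notes then say that a subject who has such disease cannot respond at all. Both cannot apply to the same patient.

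The patients caught are ordinary ones. Eligibility item 6 in Section 3.2 asks for measurable disease and does not exclude further lesions. Such patients stay in the denominator of 25 or 53 but, under the literal text, cannot enter the numerator. If some assessors follow the notes and others the criteria, identical patients are classified differently. Either way, the count that drives the stage 1 rule and the final decision is affected.

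Central review would not catch the error. Sections 8.2 and 8.4 send scans for central response review when a response has been seen, and Section 8.4 specifies as assessed locally. A patient whom the site caps at stable disease is not sent. Section 8.2 also triggers the early repeat MRI only after a CR or PR, so a capped patient does not get that confirming scan and may be hard to reclassify later.

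**Working it through.** **1. The text applied to two hypothetical patients.**

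| Patient | Status under Section 8.1 | Listed PR criteria | PR note as written |
|---|---|---|---|
| Three 2 cm enhancing lesions, each area product down 80% | Two followed; the third is non-measurable despite its size | Lesion criteria (a) and (b) met: 80% exceeds 50%, no progression | Stable disease at best |
| One 3 cm lesion down 80%, one unchanged 7 mm satellite | Satellite is below 1 cm x 1 cm, so non-measurable | Lesion criteria (a) and (b) met | Stable disease at best |

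The remaining PR conditions (no new lesions, steroids, T2/FLAIR, clinical status) are assumed to be met. The two right-hand columns disagree for both patients.

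**2. The plan's own power figures.** Inputs from Section 11:

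- Arm A: 15 then 25 patients, stop at 0/15, reject at 4 or more of 25, 5% versus 25%.
- Arm B: 24 then 53 patients, stop at 7 or fewer of 24, reject at 22 or more of 53, 30% versus 50%.

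With X1 the stage 1 responses, r1 the stopping limit and r the rejection limit:

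P(reject) = sum over x1 > r1 of P(X1 = x1; n1, p) × P(Bin(n − n1, p) ≥ r − x1)

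- Arm A: alpha 0.034, power 0.901, early stopping 0.463 (null) and 0.013 (alternative).
- Arm B: alpha 0.047, power 0.902, early stopping 0.565 (null) and 0.032 (alternative).

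The plan states 90% power, 5% false positives, and stopping probabilities of 0.46/0.01 and 0.57/0.03. The design arithmetic is sound; the fault is in the endpoint definition.

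**3. Effect of barring some responders.** Let h be the share of would-be responders assessed by HGG RANO and g the share of those who carry a non-measurable lesion. The fraction barred is f = h × g, and the effective response rate is p1 × (1 − f). The documents give neither h nor g. Taking h = 0.5 and g = 5%, 10% and 20%, all assumed, gives f = 2.5%, 5% and 10%.

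| f | Arm A rate | Arm A power | Arm A stage 1 shortfall | Arm B rate | Arm B power | Arm B stage 1 shortfall |
|---|---|---|---|---|---|---|
| 0 | 25.0% | 0.901 | 0.013 | 50.0% | 0.902 | 0.032 |
| 2.5% | 24.4% | 0.888 | 0.015 | 48.75% | 0.868 | 0.042 |
| 5% | 23.75% | 0.874 | 0.017 | 47.5% | 0.826 | 0.054 |
| 10% | 22.5% | 0.843 | 0.022 | 45.0% | 0.721 | 0.086 |

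Every row assumes that all assessors apply the notes literally. Partial uptake gives a smaller f.

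**4. Direction.** The notes can only remove responders. If the true rate equals the null and 10% of responders are barred, the false positive rate falls from 0.034 to 0.024 in Arm A and from 0.047 to 0.015 in Arm B.

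**The case against.** The strongest reply is that a sensible reader would supply the missing word. Four listed criteria and the closing sentence on measurable disease in Section 8.1 presuppose that a patient with both lesion types can respond, so the notes were probably meant for patients with no measurable lesion. This stands as a statement of likely intent. A reader might infer from the notes that such patients can never be counted; the documents do not support that, because the surrounding text points the other way. But Section 8.1 sends only patients with measurable enhancing disease to HGG RANO, so under the narrow reading the notes apply to almost nobody. A reader looking for their purpose is pushed towards the broad one. The ambiguity remains.

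A reader might also take 20% of all responders as the share barred, which gives power of 0.44 in Arm B and 0.76 in Arm A. That is a stacked worst case. Arms A and B enrol grade II–III disease and admit non-enhancing tumours, which LGG RANO assesses without any such note. With half of responders under HGG RANO, f = 20% needs 40% of those to carry a non-measurable lesion, and every assessor to read the notes literally.

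Two further points stand. The Imaging Core Manual, with which Section 8 requires compliance, was not among the documents and may settle the lesion rules, so it cannot be said that nothing corrects the notes. And a stage 1 shortfall is not always final: under Section 11, a significant reduction in FLAIR growth rate sends the arm to CTEP review, so the shortfall probabilities are upper bounds on wrongful stopping.

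**Conclusion.** The contradiction is real and can be seen from the protocol alone. As written, the notes bar from CR and PR patients who have measurable enhancing disease plus a third lesion or a sub-centimetre one; at best, such patients will be classified inconsistently. This concerns the primary endpoint, but only for patients assessed by HGG RANO.

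The size is a sensitivity range, not an estimate. Over 2.5% to 10% of all would-be responders barred, power runs from 0.87 to 0.72 in Arm B and from 0.89 to 0.84 in Arm A. It rests on an assumed HGG share, an assumed frequency of such lesions and full literal uptake. Arm B is the more sensitive. The bias works against an active regimen and cannot inflate the false positive rate.

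**What to change.** - In both notes of Section 8.1.1, insert *only* after the reference to non-measurable disease, so that the cap at stable disease applies to subjects with no measurable enhancing lesion.
- In Section 8.1, add one sentence: enhancing lesions beyond the two followed must disappear for CR and must not progress for PR, but do not by themselves limit the response to stable disease.
- Check the Imaging Core Manual for the same wording and align it.
- Make the change before responses are adjudicated. If any have been already, re-read the HGG RANO patients recorded as stable disease who had more than two lesions or a small extra lesion.

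The wording change costs one word in two places and one sentence, with no added scans or patients and no change to sample size or decision rules.
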